9. MONITORING PLAN

During the investigation representatives from Oticon Medical will have regular contacts with the investigation site. Authorized representatives of the sponsor and/or regulatory authority and/or independent ethics committees may visit the centre to perform audits/inspections, including source data verification. The extent of the monitoring will be outlined in a study specific monitoring plan.

10. INVESTIGATION ADMINISTRATIVE STRUCTURE

In this sponsor initiated study, Oticon Medical AB is the sponsor.

10.1 Information to be supplied to the clinical investigator

Before initiating the clinical investigation, the clinical investigator will receive written study and device related information, as well as being trained in the study procedure etc. The devices used in this study are already a CE marked product. If the investigator needs additional material about the device that is not covered in the product information and use materials, Oticon Medical will oblige to the request and provide as much information as possible.

10.2 Agreement between the clinical investigator and Oticon Medical

A contract between Oticon Medical and the investigators will be agreed upon for the terms of performing this study. The investigators/clinics will be given access to the equipment needed to perform measurements specific to the study.

The investigators and their clinics receive no other compensation from Oticon Medical besides what has been agreed upon in the study contract and have no further economic interest in the project other than what has been stated above.

The participants of the study will be reimbursed for the travel expenses and will not receive further compensation.

10.3 The patient's medical record

The patient's participation in the clinical investigation will be reported in the patient's medical record along with patient code, title of the investigation and investigation code. All diagnoses of

relevance for the investigation, all patient visits, including those that only are relevant for the clinical investigation and all adverse events shall also be documented. It will also be documented that the patient has been informed about the study and that the patient has signed the informed consent form. The date of inclusion into the study will be recorded together with the study code. The date when the patient leaves the study will be recorded.

10.4 Data handling

All data concerning trial subjects is protected under the Act on Processing of Personal Data, the Health Act, and the EU General Data Protection Regulation (GDPR) and will be handled accordingly. All information about the subjects is under professional secrecy. All information about the subjects outside the clinic will be anonymized and the subjects' identity will not be known for anyone outside the clinic.

10.5 Suspension or premature termination of the clinical investigation

If the investigation is terminated prematurely or suspended, the sponsor will promptly inform the clinical investigation center of the termination or suspension and the reason(s) for this. The ethics committee will also be informed promptly in writing and provided with the reason(s) for the termination or suspension by the sponsor. The sponsor may at any time terminate the clinical investigation due to circumstances related to the product or company that preclude ongoing patient treatment.

11. DATA MANAGEMENT

Data captured will be recorded in the electronic Case Report Forms (eCRF), as well as on the test computer. All data must be accurately recorded in the eCRF. A source data verification list will be agreed on for data verification. A paper version of the CRF (worksheet) will be made available to be used for recording source data. The site will store the paper CRF; the sponsor may request a copy for remote monitoring. Other sources such as patient chart will also be used as source data. All patients will be given a code and should not have names and other personal identification information on eCRFs/CRF to make sure that the patient's identity remains unknown to external parties such as the Sponsor and auditor. It is the responsibility of the investigator to make sure that patient identification listings with patient code and identity are kept in a separate location than the participant folder. Personal information shall be securely stored by the site for 5 years after the study has been completed. The research data (nonidentifiable) will be kept for 20 years after the completion of the study.

11.1 Data Entry and Management

Data entry to the eCRF (online system: Smart Trial) will be performed by the investigator and the study team. Data handling, data cleaning and statistics will be performed by Oticon Medical AB or external parties such as a CRO or a statistician whom Oticon Medical AB may have a contract with for assistance. In case of the external party being contracted for data management, this organization may, as needed, gather advice from an independent clinical specialist.

	Title Assessing listening effort at different signal-to-noise ratios in bone-anchored users	Document no Doc-00064398	Revision 1	Page 22(33)
---	---	------------------------------------	----------------------	-----------------------

11.1.1 Data management procedures, if done

Once all the data has been entered and has been reviewed by the monitor/clinical trial manager/data manager with all the pending information about the missing data satisfactorily explained, database lock will be agreed by clinical trial manager and/or data manager, principal investigator, and study project leader in a clean file meeting before any data analysis.

11.1.2 Confidentiality

At all times throughout the clinical investigation confidentiality will be observed by all parties involved. All data will be secured against unauthorized access. The principal investigator will provide direct access to source data during and after the clinical investigation for monitoring, audits, EC review and regulatory authority inspections. Permission for direct access to source documents from the subject, hospital administration and national regulatory authorities shall be obtained by the principal investigator, as per national regulations, before starting the clinical investigation.

12. STATISTICAL CONSIDERATIONS

The analysis of the primary endpoint will be performed via Growth Curve Analysis (Mirman, 2014) to compare the overall pupil dilation for OSN ON vs. OFF at +4 dB SNR. Growth Curve Analysis will also be used to evaluate differences in overall pupil dilation between OSN ON and OSN OFF at different SNRs, between OSN Auto and OSN OFF (before and after field trial), and between OSN Auto and OSN ON at +4 dB SNR.

Additionally, a mixed-model ANOVA (SNR and OSN setting as fixed factors; subject as random factor) will be used to analyze the peak pupil dilation (PPD) across SNRs. Only data of those patient that completed both Visit 1 and Visit 2 will be included in the final analysis. When applicable, post-hoc analysis will be performed via contrasts of least-square means to clarify at which SNRs the effect of OSN is significant (the p-values will be corrected for multiple comparisons using the Tukey method).

A mixed-model ANOVA (SNR and OSN setting as fixed factors; subject as random factor) will also be used to analyze the speech recognition scores across SNRs. When applicable, post-hoc analysis will be performed via contrasts of least-square means to clarify at which SNRs the effect of OSN is significant (the p-values will be corrected for multiple comparisons using the Tukey method).

A mixed model ANOVA will also be used to analyze the SSQ scores for Ponto 4 vs. own device, as well as for Ponto 4 at 1-month follow up vs. 3-months follow up.

A paired t-test or Wilcoxon sign-rank test will be used to compare the NfR scores with Ponto 4 compared to own device. Pearson's or Spearman's correlation between NfR scores and pupil dilation with Ponto 4 after field trial will be performed.

A Wilcoxon sign-rank test (two tailed) will be performed for each item of the preference questionnaire to test whether the distribution of the scores is significantly different than "No preference".

On all tests a significance level of 5% will be adopted. Correction for multiple comparisons will be performed where applicable.

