7. DESIGN OF THE CLINICAL INVESTIGATION

This study is a single-center, single-blinded, prospective study on adults BAHS users, who are already experienced Ponto users (see inclusion criteria).

All participants will perform a speech-in-noise test at different SNRs and at three different Ponto 4 settings (OSN ON, OSN OFF, OSN Auto) while an eye-tracking camera records pupil dilation as an indicator of listening effort. The patients are blinded to the test condition. Patients that are bilaterally implanted, will be tested bilaterally with a Ponto 4 placed on each abutment. Patients that are unilaterally implanted will be tested with a Ponto 4 on the implanted side and the opposite ear will remain open and unaided. For the unilaterally fitted patients, no crucial contribution from the opposite side is expected to occur since they also have a hearing loss on the opposite ear (see inclusion criteria). All participants will perform all conditions and will act as their own control.

See Appendix A and B for a list of all conditions and time estimates.

Pupillometry at Visits 1 and 2

The tested conditions will be balanced across participants and across visits (see Figure 1 and Appendix B for the details). The three OSN settings (OSN ON, OSN OFF, OSN Auto) will be tested at the same visit for the same SNR to avoid differences in pupil dilation that could occur across visits (e.g., small differences in camera positioning, lighting, fatigue,...). The order of SNRs will be randomized within each OSN settings (see Figure 1). In a best attempt to maintain motivation constant within and across visits, easy and difficult conditions will be balanced across visits (i.e., SNRs of -8 dB, 0 dB, and +8 dB at one visit; SNRs of -4 dB and +4 dB at the other visit).

Two training lists (+4 dB SNR with OSN OFF, and -4 dB SNR with OSN ON) will be performed before starting the test at Visit 1. Since Visit 2 is scheduled within a week after Visit 1, only one training list will be performed before starting the test at Visit 2.

The setting OSN Auto will only be performed at +4 dB SNR. This SNR was specifically chosen to lead to a speech intelligibility performance, on average, above 50% – hence before the “give up” point, while still activating of the OSN feature. The OSN Auto condition will be tested either at Visit 1 or Visit 2, in between the other two settings (see Figure 1).

Field-trial period

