7.1.2 Secondary endpoints

- Difference in peak pupil dilation (PPD) between OSN ON and OSN OFF across SNRs.
- Difference in speech recognition scores between OSN ON and OSN OFF across SNRs.
- Difference in overall pupil dilation, as calculated via Growth Curve Analysis, between OSN ON and OSN OFF across SNRs.
- Difference in overall pupil dilation between OSN Auto and OSN OFF at +4 dB SNR (measured at visits 1 or 2), as calculated via Growth Curve Analysis.
- Difference in overall pupil dilation between OSN Auto and OSN OFF at +4 dB SNR (measured at visit 3), as calculated via Growth Curve Analysis.
- Difference in overall pupil dilation between OSN Auto and OSN ON at +4 dB SNR (measured at visits 1 or 2), as calculated via Growth Curve Analysis.
- Difference in SSQ scores between Ponto 4 after 1 month field trial and own device.
- Difference in SSQ scores between Ponto 4 after 3 months field trial and own device.
- Difference in SSQ scores between Ponto 4 after 1-month field trial and after 3-months field trial.
- Correlation between peak pupil dilation and speech recognition scores.

- Number of test subjects preferring Ponto 4.
- Sound scenarios for which test subjects significantly prefer Ponto 4 over own device.
- Difference in dB between aided thresholds and BC in-situ thresholds –i.e., remaining air-bone gap (also known as BC gain or effective gain).

7.1.3 **Tertiary endpoints**

- Difference in NfR scores with Ponto 4 after field trial and own device.
- Correlation between NfR scores and pupil dilation with Ponto 4 after field trial.
- Difference in overall pupil dilation (intercept term) between Visit 1-2 and Visit 3 for the contrast OSN Auto vs. OSN OFF.
- Difference in peak pupil dilation between Visit 1-2 and Visit 3 for the contrast OSN Auto vs. OSN OFF.
- Difference in the following parameters between Visit 1-2 and Visit 3 for the pupil curves obtained with OSN Auto and OSN OFF: rate of growth/decay (linear term), changes in the rate of growth/decay (quadratic term), and the steepness of the curve around inflection points (cubic term).
- Difference in speech recognition scores between Visit 1-2 and Visit 3 for OSN Auto and OSN OFF.
- Correlation between pupil dilation and the patient's PTA and characteristics (e.g., age, unilateral/bilateral implantation).
- Correlation between speech recognition scores and the patient's PTA and characteristics (e.g., age, unilateral/bilateral implantation).

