12.1 Sample size calculation

The sample size calculation was based on the primary endpoint. The effect size was estimated based on the interim results of a pilot study conducted internally at Oticon Medical (Denmark) - internal study reference: BC102 - where the experimental setup was the same as in the current study. Although the speech target consisted of Danish sentences (HINT; Nielsen and Dau, 2011) instead of UK English sentences as in the current study, we expect a similar effect size. Hence, an effect size of 0.48 was estimated based on the mean and standard deviations obtained for N = 20 subjects at an SNR of +4 dB (Mean with OSN ON = 0.078; Mean with OSN OFF = 0.11; standard deviation with OSN ON = 0.09; standard deviation with OSN OFF = 0.08). These mean peak pupil dilations are in line with the results obtained in a previous study that used similar setup and conditions – although the patients wore hearing aids instead of BAHS (Wendt et al., 2017). Using a significance level of 0.05 and a statistical power of 0.8, a minimum sample size of 29 subjects was obtained. Hence, it was decided that 30 subjects should complete the primary endpoint (Visit 1 and Visit 2). If test persons are withdrawn from the study, the recruitment process will continue until 30 patients have completed Visit 1 and Visit 2.

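### Tukey is named to find the SNRs at which OSN works, but its family is not stated: within each SNR it corrects nothing across SNRs, and over all ten cells it costs much of the power

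*Combined protocol and SAP*

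**What the plan says.** Section 7.1.2 lists two secondary endpoints that matter here: "Difference in peak pupil dilation (PPD) between OSN ON and OSN OFF across SNRs" and "Difference in speech recognition scores between OSN ON and OSN OFF across SNRs". Appendix A gives five SNRs (-8, -4, 0, +4, +8 dB) for each of ON and OFF, so each outcome has ten cells and five ON-OFF contrasts.

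Section 12 describes the PPD model as "a mixed-model ANOVA (SNR and OSN setting as fixed factors; subject as random factor) will be used to analyze the peak pupil dilation (PPD) across" the SNRs, and uses the same model for speech scores. It does not name the SNR-by-OSN interaction. For each outcome it then adds a follow-up step: "When applicable, post-hoc analysis will be performed via contrasts of least-square means". The purpose given for that step, and the adjustment named for it, are "to clarify at which SNRs the effect of OSN is significant (the p-values will be corrected for multiple comparisons using the Tukey method". It does not say which means form the Tukey set, or which ANOVA result makes the step applicable. The general line that closes the section, "Correction for multiple comparisons will be performed where applicable", names no family either.

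OSN has a third setting, but Section 7 states: "The setting OSN Auto will only be performed at +4 dB SNR".

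**The concern.** Tukey's method protects all pairwise comparisons among a set of means. The stated aim is different: to find which of five SNRs show an ON-OFF difference. Two literal uses of Tukey are open, and they behave very differently. One leaves the five SNRs uncorrected against each other. The other corrects for 45 pairs, 40 of which nobody is asking about.

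These contrasts decide at which SNRs OSN will be said to reduce PPD or improve speech recognition. Section 6.2 makes an SNR-specific PPD hypothesis, so the list of significant SNRs is a result in itself. Section 7.4 (time frame) allows data from the first two visits, where every ON and OFF condition is measured, to be analysed early. The family could therefore be chosen after the data have been seen.

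**Working it through.** **Inputs.** n = 30 completers of Visits 1 and 2 (Section 12.1); 2 settings x 5 SNRs (Appendix A); 5% level (Section 12); effect size 0.48 at +4 dB, from pilot means 0.078 (ON) and 0.11 (OFF) with SDs 0.09 and 0.08 (Section 12.1). Two-sided contrasts and a model with the SNR-by-OSN interaction are assumed; Section 12 states neither.

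**The plan's own figure.** "an effect size of 0.48 was estimated based on the mean and standard deviations obtained for N = 20 subjects". A paired t-test with d = 0.48 and 80% power needs 29 subjects one-sided (power 0.810), which matches the plan's minimum; two-sided it needs 37. The match supports reading 0.48 as a paired effect. The pilot difference is 0.11 - 0.078 = 0.032, so 0.48 requires an SD of the difference of 0.032/0.48 = 0.0667. The implied ON-OFF correlation is (0.09² + 0.08² - 0.0667²)/(2 x 0.09 x 0.08) = 0.70. It is not reported.

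**Degrees of freedom.** A random-subject model on 30 x 10 observations has 29 x 9 = 261 df; a separate paired comparison has 29. Results below are given across that range where they differ.

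**Critical |t|.** The Tukey value is q(0.95; k, df)/√2.

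| Method | 261 df | 29 df |
|---|---|---|
| Unadjusted | 1.969 | 2.045 |
| Tukey, 2 means | 1.969 | 2.045 |
| Bonferroni over 5 | 2.595 | 2.756 |
| Tukey, 10 means (45 pairs) | 3.191 | 3.420 |

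With two means Tukey is exactly the t-test.

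**Error, within-SNR use.** For five independent tests, 1 - 0.95⁵ = 22.6%. Simulation gives the figures below (100,000 trials per pattern, 261 df, residual SD 0.0667/√2 = 0.0471). Each entry is the chance of at least one false result, either direction / false benefit only. The gates are 5% F tests.

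| Procedure | No OSN effect anywhere | True effect at +4 dB only, false result elsewhere |
|---|---|---|
| Within-SNR Tukey, no gate | 22.5 / 12% | 18.6 / 9.6% |
| behind OSN main effect | 3.2 / 1.6% | 5.9 / 5.7% |
| behind interaction | 4.9 / 3.1% | 12.8 / 5.2% |
| behind either term | 7.9 / 4.6% | 15.9 / 8.2% |
| Holm over five, no gate | 4.9 / 2.5% | 4.4 / 2.3% |

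Ten-cell Tukey gives 0.8% when OSN has no effect.

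**Power per SNR at d = 0.48, n = 30** (noncentral t, noncentrality 0.48 x √30 = 2.63; 29 to 261 df):

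- unadjusted: 72-75%
- Bonferroni over five: 46-51%
- ten-cell Tukey: 24-29%

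At 261 df, Holm gives about 51%, 55% and 62% when the effect is present at one, three and five SNRs; ten-cell Tukey stays at 29%.

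**Power behind a gate** (261 df). The OSN main-effect gate gives 20%, 72% and 75% in the same three patterns. The interaction gate opens in only 5% of trials if the effect is equal at all SNRs, leaving about 3% power per SNR.

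**Sensitivity to the unreported correlation** (261 df). For r = 0.5, 0.7 and 0.8, d is 0.37, 0.48 and 0.59. Ten-cell Tukey gives 13%, 29% and 51%; Bonferroni over five gives 30%, 51% and 73%.

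**The case against.** - **A gated within-SNR analysis can beat Holm on power.** This stands. With an equal effect at all five SNRs, an OSN or either-term gate gives 75% per SNR against Holm's 62%. With effects at three SNRs, the OSN gate gives 72% against 55%, with 8.3% false results in either direction (5.0% false benefit) against 3.3% for Holm. A reader might infer that every use of Tukey here is worse than a correction over five contrasts; that is not so. The gate loses when only +4 dB carries an effect (20% against 51%), and the plan does not say that it intends a gate.
- **A reader might take 22% as the plan's error rate.** The documents do not fix it. It applies only if Tukey is used within each SNR and no gate is applied. The sentence promises corrected p-values, which argues against a use that corrects nothing. The ten-cell use does honour that promise, and its fault is lost power only.
- **The sample size was set for the primary endpoint.** True, so no stated power target for these contrasts is missed. The loss is still avoidable.
- **Five may not be the right PPD family.** Section 6.2 expects a PPD benefit only below 5 dB and above the give-up point, which excludes +8 dB. A smaller family is legitimate, but that point has no numeric value in the plan, so the SNRs must be listed.
- **OSN Auto.** A reader might infer that Auto enters the model and distorts the family. Both endpoints are ON against OFF, and Section 12 assigns the Auto comparisons of overall pupil dilation to Growth Curve Analysis. Saying that Auto is outside the family is a clarification only.
- **Naming the set would be enough.** Not quite: naming two means leaves no correction across SNRs, and naming ten leaves the loss of power.

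**Conclusion.** The point holds. Tukey does not fit a question made up of five ON-OFF contrasts, and its set of means is not stated. The open readings run from about 22% family error with 72-75% power (within SNR, ungated) to about 0.8% with 24-29% power (ten cells). Gated readings lie between on error, with power that depends strongly on the gate and on where the effect is. Holm over five stays at or below 5% in every pattern tested and has more power than ten-cell Tukey in all of them. It does not have more power than every gated alternative.

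The power figures assume that 0.48 is a paired effect (implied correlation about 0.70) and applies at the SNR tested. The documents give it for +4 dB only, and give no effect size for speech scores. The error rates assume a model with the interaction and equal variances.

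Only secondary endpoints are affected. The primary comparison, overall dilation at +4 dB by Growth Curve Analysis, is a single contrast and is untouched.

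**What to change.** In both post-hoc sentences of Section 12, replace Tukey with Holm, or a single-step multivariate-t adjustment, over the five ON-OFF contrasts at -8, -4, 0, +4 and +8 dB. Use one family for PPD and a separate one for speech recognition. State that OSN Auto is outside these families and that the model includes the SNR-by-OSN interaction. Holm needs no gate, so the plan can say that the five contrasts are tested without a prior significant ANOVA term.

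If the sponsor prefers a smaller PPD family that matches the hypothesis in Section 6.2, it should list those SNRs before the data are seen.

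The cost is two sentences and the matching code, with no new data, visits or patients. The downside is less power than no correction: about 51% against 75% at +4 dB if d = 0.48 (261 df). The change does not cover the Growth Curve comparisons across SNRs, for which Section 12 names no specific correction method.

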12.1 Sample size calculation

The sample size calculation was based on the primary endpoint. The effect size was estimated based on the interim results of a pilot study conducted internally at Oticon Medical (Denmark) - internal study reference: BC102 - where the experimental setup was the same as in the current study. Although the speech target consisted of Danish sentences (HINT; Nielsen and Dau, 2011) instead of UK English sentences as in the current study, we expect a similar effect size. Hence, an effect size of 0.48 was estimated based on the mean and standard deviations obtained for N = 20 subjects at an SNR of +4 dB (Mean with OSN ON = 0.078; Mean with OSN OFF = 0.11; standard deviation with OSN ON = 0.09; standard deviation with OSN OFF = 0.08). These mean peak pupil dilations are in line with the results obtained in a previous study that used similar setup and conditions – although the patients wore hearing aids instead of BAHS (Wendt et al., 2017). Using a significance level of 0.05 and a statistical power of 0.8, a minimum sample size of 29 subjects was obtained. Hence, it was decided that 30 subjects should complete the primary endpoint (Visit 1 and Visit 2). If test persons are withdrawn from the study, the recruitment process will continue until 30 patients have completed Visit 1 and Visit 2.

